4.5.1 Primary Endpoints

The primary study endpoints are (1) the overall response rate (ORR) of patients with advanced cholangiocarcinoma receiving a combination of pembrolizumab and olaparib, which directly assesses whether this drug combination yields a clinically meaningful result in this group of patients—as per the rationale stated in the paragraph above; and (2) the safety and tolerability of combined pembrolizumab and olaparib in patients with advanced cholangiocarcinoma as measured by adverse events, which will help to rationally validate any apparent clinical improvement observed.

4.5.2 Secondary Endpoints

The secondary study endpoints are the duration of response (DOR), progression free survival (PFS), and overall survival (OS) in patients receiving the combination therapy. All of these endpoints are part of the clinical response assessment.

Primary Endpoint Definition

1. The objective response rate (ORR) is the proportion of all subjects with confirmed PR or CR according to RECIST 1.1, from the start of treatment until disease progression/recurrence (taken as reference for progressive disease, the smallest measurements recorded since the start of treatment).

Secondary Endpoint Definition

1. PFS is defined as the duration from the date of registration until disease progression (as defined above; using RECIST 1.1) or death occurs. Subjects who have not progressed will be right-censored at the date of the last disease evaluation.
2. OS is defined as the time of registration until death as a result of any cause.
3. Overall response rate (ORR) is defined as the sum of complete response (CR) + confirmed partial response (PR) and will be determined using the immune-related response criteria (iRECIST).
4. Grade 3 and 4 toxicities as defined by the NCI Common Terminology Criteria for Adverse Events (NCI CTCAE) v4.

4.5.3 Rationale for Exploratory (Biomarker) Endpoints

Given the low expression of the ERCC1 protein in the majority of cholangiocarcinomas, together with relative frequent IDH1/2 mutations found in these tumor types, we hypothesize that the combination of PARP inhibition and immune checkpoint blockade will produce a durable anti-tumor response against cholangiocarcinoma by synergistically inducing DNA damage, increasing tumor antigen number and producing durable immune response against cholangiocarcinoma. Therapies that target the programmed death-1 (PD-1) receptor have shown unprecedented rates of

A Phase II, Single-arm Study of Combination Pembrolizumab and Olaparib in the Treatment of Patients with Advanced Cholangiocarcinoma

Version 2.1: 17Mar2023

durable clinical responses in a sub-group of patients with various cancer types [1-5]. Biomarkers in patient tumor that will predict response to anti-PD-1 therapy are being actively investigated. One mechanism by which cancer tissues limit the host immune response is via upregulation of PD-1 ligand (PD-L1) and its ligation to PD-1 on antigen-specific CD8+ T cells [6, 7]. Recent research has reported that tumor regression after therapeutic PD-1 blockade requires pre-existing CD8+ T cells that are negatively regulated by PD-1/PD-L1-mediated adaptive immune resistance [8].

We propose that olaparib will increase the response of pembrolizumab by inducing DNA damage, increasing tumor antigen number, and producing durable immune response against cholangiocarcinoma. We expect that cancer cells with low expression of the ERCC1 proteins or with IDH1/2 mutations will have more DNA damage upon olaparib treatment than cancer cells that have normal expression of the ERCC1 protein, or are without IDH1/2 mutations.

In this study, we will first test whether the effect of olaparib and pembrolizumab treatment on tumor infiltrating lymphocytes, the level of PD-1 and PD-L1 expression, and clonality of the T-cell repertoire differs between low ERCC1/IDH1/2 mutant and normal ERCC1/non IDH1/2 mutant tumor cells. Then we will examine whether the change of tumor infiltrating lymphocytes and the level of PD-1 and PD-L1 expression correlates with clinical response in patients treated with pembrolizumab and olaparib combination therapy.

5.0 METHODOLOGY

5.1 Study Population

This trial is a single institution study, enrolling patients with cholangiocarcinoma, biliary cancers manifesting as either intrahepatic, extrahepatic or gallbladder cancer, that is unresectable, metastatic, or has either failed to respond to or demonstrated progression despite prior 1st line therapy. Patients with ampullary cancers are excluded. Patients must be, in the opinion of the site investigator, appropriate candidates for experimental therapy. Patients should be evaluated for the need to undergo biliary drainage by stent placement prior to study participation. Patients should have adequate biliary drainage with no unresolved biliary obstruction.

The target recruitment for this study is 36 patients. As the trial is opening at several centers, recruitment is anticipated to take 21 months, and the anticipated time to complete follow-up of all patients will be 36 months.

5.2 Inclusion Criteria

Subject must meet all of the following applicable inclusion criteria to participate in this study:

1. Be willing and able to provide written informed consent/assent for the trial.
2. Be ≥ 18 years of age on day of signing informed consent.

A Phase II, Single-arm Study of Combination Pembrolizumab and Olaparib in the Treatment of Patients with Advanced Cholangiocarcinoma

Version 2.1: 17Mar2023

3. Patients must have received 1 line of prior systemic therapy for metastatic or resectable disease (i.e. patients may have received adjuvant gemcitabine and then later platin-based therapy for recurrent metastatic disease)
4. Histological confirmation of cholangiocarcinoma manifesting as either intrahepatic, extrahepatic or gallbladder cancer. Patients with ampullary cancer are excluded.
5. Have measurable disease based on RECIST 1.1.
6. Be willing to provide tissue from a newly obtained core or excisional biopsy of a tumor lesion. Newly obtained is defined as a specimen obtained up to 6 weeks (42 days) prior to initiation of treatment on Day 1. Subjects for whom newly obtained samples cannot be provided (e.g. inaccessible or subject safety concern) may submit an archived specimen only upon agreement from the sponsor-investigator. Subjects from whom a biopsy is not medically possible or safe may be enrolled on the study upon agreement from the principal investigator.
7. Have a performance status of 0 or 1 on the ECOG Performance Scale.
8. Demonstrate adequate organ function as defined in Table 1. All screening labs will be performed within 28 days of registration.

Table 1: Adequate Organ Function Laboratory Values

System	Laboratory Value
Hematological	
Absolute neutrophil count (ANC)	$\geq 1,500 / \mu\text{L}$
Platelets	$\geq 100,000 / \mu\text{L}$
Hemoglobin	$\geq 9 \text{ g/dL}$ or $\geq 5.6 \text{ mmol/L}$ without transfusion or EPO dependency (within 7 days of assessment)
Renal	
Serum creatinine OR Measured or calculated ^a creatinine clearance (GFR can also be used in place of creatinine or CrCl)	$\leq 1.5 \times$ upper limit of normal (ULN) OR $\geq 50 \text{ mL/min}$ for subject with creatinine levels $> 1.5 \times$ institutional ULN
Hepatic	

A Phase II, Single-arm Study of Combination Pembrolizumab and Olaparib in the Treatment of Patients with Advanced Cholangiocarcinoma
 Version 2.1: 17Mar2023

Serum total bilirubin	$\leq 2.0 \times \text{ULN}$
AST (SGOT) and ALT (SGPT)	$\leq 3.0 \times \text{ULN}$ OR $\leq 5 \times \text{ULN}$ for subjects with liver metastases
Albumin	$\geq 2.5 \text{ mg/dL}$
Coagulation	
International Normalized Ratio (INR) or Prothrombin Time (PT)	$\leq 1.5 \times \text{ULN}$ unless subject is receiving anticoagulant therapy as long as PT or PTT is within therapeutic range of intended use of anticoagulants
Activated Partial Thromboplastin Time (aPTT)	$\leq 1.5 \times \text{ULN}$ unless subject is receiving anticoagulant therapy as long as PT or PTT is within therapeutic range of intended use of anticoagulants
aCreatinine clearance should be calculated per institutional standard.	

- Female subject of childbearing potential should have a negative urine or serum pregnancy within 72 hours prior to receiving the first dose of study medication. If the urine test is positive or cannot be confirmed as negative, a serum pregnancy test will be required.
- Female subjects of childbearing potential should be willing to use 2 methods of birth control or be surgically sterile, or abstain from heterosexual activity for the course of the study through 120 days after the last dose of study medication (Reference Section in Appendix 3). Subjects of childbearing potential are those who have not been surgically sterilized or have not been free from menses for > 1 year.
- Male subjects should agree to use an adequate method of contraception starting with the first dose of study therapy through 120 days after the last dose of study therapy.

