1.0 TRIAL SUMMARY

Abbreviated Title	Combination Pembrolizumab and Olaparib in the Treatment of Patients with Advanced Cholangiocarcinoma
Trial Phase	II
Clinical Indication	Advanced cholangiocarcinoma who have failed or cannot tolerate 1 st line systemic therapy
Trial Type	Single arm, single-site
Type of control	None
Route of administration	Oral and intravenous
Trial Blinding	None
Treatment Groups	Olaparib plus pembrolizumab
Number of trial participants	36
Estimated enrollment period	24
Estimated duration of trial	36
Duration of Participation	12
Estimated average length of treatment per patient	12

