2.0 TRIAL DESIGN

2.1 Trial Design

We propose an open label, one-arm study to assess the safety and efficacy of olaparib and pembrolizumab in patients with cholangiocarcinoma who have progressed on or cannot tolerate gemcitabine-based therapy.

The primary objective of the study is to assess the ORR of patients with advanced cholangiocarcinoma receiving a combination of pembrolizumab and olaparib. It is hypothesized that the addition of olaparib will improve the response rate of second line systemic therapy from 17.5% to 35% in patients with advanced cholangiocarcinoma.

The study is designed to enroll 33 subjects (for 85% power) with advanced stage cholangiocarcinoma to test the hypothesis that the combination of olaparib and pembrolizumab will increase the ORR in comparison with the ORR from second line systemic chemotherapy (historical control) in this patient population. As our primary study endpoint, which is also being used to determine the sample size of the study, we propose that the combination of olaparib and pembrolizumab will increase the ORR to 35% from 17.5% (achieved with systemic cytotoxic chemotherapy including mFOLFOX—historical control). To allow a 10% patient drop off rate, we expect to enroll a total of 36 subjects into this study. In addition, as secondary study endpoints we expect to see an increase in the PFS and OS of patients receiving combination therapy compared to cytotoxic chemotherapy.

[figure not shown]
A Phase II, Single-arm Study of Combination Pembrolizumab and Olaparib in the Treatment of Patients with Advanced Cholangiocarcinoma
Version 2.1: 17Mar2023

In this study, we propose the collection of three biopsies—one at baseline prior to the start of treatment, one at the beginning of week 4, three weeks after the administration of combination olaparib and pembrolizumab, and one at the time of cancer progression—for the elucidation of exploratory study endpoints. Patients will have a CT or MRI scan at the beginning of treatment and then every 6 weeks thereafter for the first six months of study treatment administration, then every 9 weeks for up to 12 months after the start of treatment, followed by every 12 weeks up to 24 months on study. All patients will continue to receive olaparib and pembrolizumab combination treatment as tolerated unless unacceptable toxicities or cancer progression occur, at which time therapy will cease. In the absence of any problems, the planned study duration is 20-36 months.

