8.0 STATISTICAL ANALYSIS PLAN

8.1 Statistical Analysis Plan Summary

8.1.1 Statistical Methods

8.1.1.1 Study Design

This is an open-label, single-arm, Phase II safety and efficacy study of combination therapy with pembrolizumab and olaparib in patients with advanced cholangiocarcinoma who have progressed on or cannot tolerate frontline chemotherapy.

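### Inclusion item 3 requires neither progression on nor intolerance of the prior line, so the criteria admit patients outside the second-line population behind the 17.5% null

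*Combined protocol and SAP*

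**What the plan says.** The list in section 5.2 is binding: "Subject must meet all of the following applicable inclusion criteria to participate in this study". Its only item on earlier treatment, item 3, reads "Patients must have received 1 line of prior systemic therapy for metastatic or resectable disease" and adds as an example that "patients may have received adjuvant gemcitabine and then later platin-based therapy for recurrent metastatic disease".

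Section 5.1 describes disease "that is unresectable, metastatic, or has either failed to respond to or demonstrated progression despite prior 1st line therapy".

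Other sections describe a narrower population:
- Section 1.0, clinical indication: "Advanced cholangiocarcinoma who have failed or cannot tolerate" first-line systemic therapy.
- Section 2.1: "patients with cholangiocarcinoma who have progressed on or cannot tolerate gemcitabine-based therapy".
- Section 8.1.1.1: "patients with advanced cholangiocarcinoma who have progressed on or cannot tolerate frontline chemotherapy".
- Section 3.2 frames its PFS and OS hypothesis around failure of frontline therapy, through progression or intolerance.

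Sections 2.1 and 4.5 attribute the 17.5% historical response rate to second-line systemic chemotherapy.

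**The concern.** The trial has one arm and no control, so its efficacy conclusion rests on comparing the observed response rate with a fixed 17.5%. That comparison can be interpreted only if the enrolled patients resemble those who produced the 17.5%.

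Section 7.1.1.2 has eligibility checked against the inclusion and exclusion criteria. Where those criteria are looser than the design text, the looser text decides who enters. Two kinds of patient meet the list without belonging to the described population:
- a patient whose disease was stable on a first line that was tolerated;
- a patient whose only systemic therapy was adjuvant, however long before recurrence. This patient would receive the trial drugs as the first treatment for advanced disease.

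Item 3 is also unclear on the count. Its example, adjuvant gemcitabine followed by platinum-based treatment at recurrence, can be read as two regimens under a one-line rule. Two screeners could classify the same patient differently.

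**Working it through.** **1. Does any criterion supply the missing condition?**

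| Place | Failure or intolerance required? | Gemcitabine-based? |
|---|---|---|
| 1.0 Trial Summary | Yes | No, first line only |
| 2.1 Trial Design | Yes (progression or intolerance) | Yes |
| 3.2 Secondary hypothesis | Yes | No, frontline only |
| 8.1.1.1 Study Design | Yes (progression or intolerance) | No, frontline only |
| 5.1 Study Population | No: failure is one alternative in a list joined by *or*; intolerance absent | No |
| 5.2 item 3 | No | No |
| 5.2 other items, 5.3 | No | No |

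The nearest exclusion is item 7 of 5.3, which asks for two weeks off prior chemotherapy and recovery from its toxicity. It does not ask why that chemotherapy stopped.

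**2. Reproduce the plan's own error rates.** Inputs from section 8.1.1.3: stage 1 has 13 patients and stops at 2 or fewer responses; the final total is 33, and the null is not rejected at 8 or fewer. For a true response rate p,

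P(success | p) = Σ (x = 3 to 13) P[Bin(13, p) = x] × P[Bin(20, p) ≥ 9 − x].

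- p = 0.175: 0.0922, matching the stated 0.092.
- p = 0.35: 0.8084, so type II error is 0.1916, matching the stated 0.192.

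The rule was therefore built on 17.5% against 35%. (The same section also prints 0.05 and 0.25 as the hypotheses, which do not fit this rule. That is a separate matter.)

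**3. Sensitivity to the population.** Suppose the treatment adds nothing, but the enrolled mix has a response rate other than 17.5%.

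| True null rate of enrolled mix | P(false success) |
|---|---|
| 17% | 0.080 |
| 17.5% | 0.092 |
| 18.25% | 0.113 |
| 20% | 0.171 |
| 21% | 0.209 |

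The upward rows can be read as mixtures. If a share f of patients lies outside the second-line population and responds at rate q, then p = (1 − f) × 0.175 + f × q.
- f = 10%, q = 25%: 0.9 × 0.175 + 0.1 × 0.25 = 0.1825.
- f = 20%, q = 30%: 0.8 × 0.175 + 0.2 × 0.30 = 0.20.
- f = 20%, q = 35%: 0.8 × 0.175 + 0.2 × 0.35 = 0.21.

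Both f and q are assumptions; the documents give neither. If q is below 17.5%, p falls and so does the error, as the 17% row shows.

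**The case against.** **The intended population is stated repeatedly, and other text narrows the gap.** Item 5 of 5.2 requires measurable disease, so a patient resected and given only adjuvant therapy would ordinarily have to have recurred. Section 5.1 asks for the investigator's judgement that experimental therapy is appropriate. Section 11.5 limits enrolment to advanced cancer without curative options and describes the alternatives as another phase II trial or non-standard therapy, which hardly fits a patient still benefiting from first-line treatment. This stands in part: the problem is a conflict between passages, not a total omission. But section 11.5 is an ethics statement outside the criteria, and none of these provisions requires progression or intolerance.

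**A reader might infer that item 3 admits patients with resectable disease.** The documents do not support that. The word describes what the prior therapy was given for, and it may be a slip for *unresectable*. Correcting the word would still not add the missing condition.

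**A reader might infer that the wording inflates the false-positive rate.** That is too strong. No response rate is given for patients who have not failed first line, and the ambiguous line count could also let in more heavily treated patients, who might respond less often. The error figures further depend on 17.5% being right for everyone else. Section 4.5 also reports a pooled second-line rate of 3.4%. With that in place of 17.5%, the mixtures run from 0.9 × 3.4% + 0.1 × 25% = 5.6% to 0.8 × 3.4% + 0.2 × 35% = 9.7%, and the rule's false-success probability is only about 0.00005 to 0.003. This objection stands in full: neither direction nor size is established.

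**Conclusion.** The conflict is real and should be resolved. Followed as written, 5.1, 5.2 and 5.3 admit patients who have neither progressed on nor failed to tolerate a first line, while 1.0, 2.1, 3.2 and 8.1.1.1 describe only patients who have, and the null rate is attributed to second-line treatment.

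The consequence is a comparison that may not be like with like. Its bias could run either way. The range of 0.080 to 0.209 for true null rates of 17% to 21% shows that the decision rule is sensitive to small shifts: an enrolled mix only 2.5 points above 17.5% takes the error to 0.171, against the plan's 0.1 target. It is not an estimate of what will happen in this trial. It assumes the 2/13, 8/33 rule is applied exactly and that the treatment adds nothing.

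**What to change.** Restate item 3 of 5.2 and the description in 5.1 in the same words, reconciled with 2.1 and 8.1.1.1: advanced (unresectable or metastatic) disease, **and** documented progression on, or intolerance of, one prior systemic line. In the same amendment:

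- State how adjuvant therapy counts as a line, including whether the interval to recurrence matters, and align the example in item 3 with that rule.
- Settle whether the prior line must be gemcitabine-based. Section 2.1 says so; 1.0 and 8.1.1.1 do not.
- Do not simply change *or* to *and* in 5.1. Read literally, that would require disease to be both unresectable and metastatic, and it would leave out intolerant patients, whom 5.1 does not mention.

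For patients already enrolled, report prior-line status and the reason the prior line stopped, so that readers can see how many fall outside the intended population.

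The cost is an eligibility wording amendment that may exclude a few patients. The sample size and decision rule are unchanged.

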5.3 Subject Exclusion Criteria

The subject must be excluded from participating in the trial if the subject:

- A history of anaphylaxis to olaparib
- Is currently participating and receiving study therapy or has participated in a study of an investigational agent and received study therapy or used an investigational device within 4 weeks of the first dose of treatment.

A Phase II, Single-arm Study of Combination Pembrolizumab and Olaparib in the Treatment of Patients with Advanced Cholangiocarcinoma

Version 2.1: 17Mar2023

3. A woman of childbearing potential (WOCBP) who has a positive urine pregnancy test within 72 hours prior to 1st dose of treatment (see Appendix 3). If the urine test is positive or cannot be confirmed as negative, a serum pregnancy test will be required.
4. Has a known history of active TB (Bacillus Tuberculosis).
5. Has known hypersensitivity to pembrolizumab or any of its excipients.
6. Has had a prior anti-cancer monoclonal antibody (mAb) within 4 weeks prior to study Day 1 or who has not recovered (i.e., \leq Grade 1 or at baseline) from adverse events due to agents administered more than 4 weeks earlier.
7. Has had prior chemotherapy, targeted small molecule therapy, or radiation therapy within 2 weeks prior to study Day 1 or who has not recovered (i.e., \leq Grade 1 or at baseline) from adverse events due to a previously administered agent.

NOTE: Subjects with \leq Grade 2 neuropathy are an exception to this criterion and may qualify for the study.

NOTE: If subject received major surgery, they must have recovered adequately from the toxicity and/or complications from the intervention prior to starting therapy.

8. Has a known additional malignancy that is progressing or requires active treatment. Exceptions include basal cell carcinoma of the skin or squamous cell carcinoma of the skin that has undergone potentially curative therapy or in situ cervical cancer.
9. Has known active central nervous system (CNS) metastases and/or carcinomatous meningitis. Subjects with previously treated brain metastases may participate provided they are stable (without evidence of progression by imaging for at least four weeks prior to the first dose of trial treatment and any neurologic symptoms have returned to baseline), have no evidence of new or enlarging brain metastases, and are not using steroids for at least 7 days prior to trial treatment. This exception does not include carcinomatous meningitis, which is excluded regardless of clinical stability.
10. Has active autoimmune disease that has required systemic treatment in the past 2 years (i.e. with use of disease modifying agents, corticosteroids, or immunosuppressive drugs). Replacement therapy (e.g., thyroxine, insulin, or physiologic corticosteroid replacement therapy for adrenal or pituitary insufficiency, etc.) is not considered a form of systemic treatment.
11. Has known history of, or any evidence of active, non-infectious pneumonitis.
12. Has an active infection requiring systemic therapy.
13. Has a history or current evidence of any condition, therapy, or laboratory abnormality that might confound the results of the trial, interfere with the subject's participation for the full

A Phase II, Single-arm Study of Combination Pembrolizumab and Olaparib in the Treatment of Patients with Advanced Cholangiocarcinoma

Version 2.1: 17Mar2023

duration of the trial, or is not in the best interest of the subject to participate, in the opinion of the site investigator.

14. Has known psychiatric or substance abuse disorders that would interfere with cooperation with the requirements of the trial.
15. Is pregnant or breastfeeding, or expecting to conceive or father children within the projected duration of the trial, starting with the pre-screening or screening visit through 120 days after the last dose of trial treatment.
16. Has received prior therapy with an anti-PD-1, anti-PD-L1, or anti-PD-L2 agent.
17. Has a diagnosis of immunodeficiency or is receiving chronic systemic steroid therapy (in dosing exceeding 10 mg daily of prednisone equivalent) or any other form of immunosuppressive therapy within 7 days prior to the first dose of study drug.
18. Has known active Hepatitis B without HBV treatment (HBV infection with ongoing HBV treatment is allowed); chronic Hepatitis C infection is allowed. Any patient receiving treatment for HCV should wait at least 14 days after completion of HCV treatment before beginning study treatment. No patient should receive HCV treatment while receiving study treatment. Note: no testing for Hepatitis B and Hepatitis C is required unless mandated by local health authority.
19. Has received a live vaccine within 30 days prior to the first dose of study drug. Examples of live vaccines include, but are not limited to, the following: measles, mumps, rubella, varicella/zoster (chicken pox), yellow fever, rabies, *Bacillus Calmette–Guérin* (BCG), and typhoid vaccine. Seasonal influenza vaccines for injection are generally killed virus vaccines and are allowed; however, intranasal influenza vaccines (e.g., FluMist®) are live attenuated vaccines and are not allowed.

